APPENDIX 1. SCHEDULE OF STUDY VISITS

	VISIT 1	VISIT 2 – SLEEP STUDY	VISIT 3	VISIT 4	VISIT 5
Informed Consent	X				
Medical History	X				
Study Inclusion/Exclusion	X				
Concomitant Medication Review	X	X	X	X	X
Wean off current wake- promoting medicines	X				
Adverse Experiences		X	X	X	X
Participant Payment	X				X
PSG/MSLT sleep study		X			
Sleepy Packet	X				
Sleep Inertia Questionnaire	X	X	X	X	X
Epworth Severity Scale	X	X	X	X	X
CGI- Baseline Questionnaire	X	X	X	X	X
CGI- Sleep Inertia Questionnaire	X	X	X	X	X
CGI- Sleepiness Questionnaire	X	X	X	X	X
CGI- Cognitive Dysfunction Questionnaire	X	X	X	X	X
Treatment Questionnaire	X	-	X	X	X
Treatment Comparison Questionnaire	X	-	X	X	X
Study Drug Titration Reviewed	X				
Randomization	X	OR X			
Dispensing or Administration of Study Drug	X	OR X	X	X	
Counting of Returned Study Drug			X	X	X

Informed Consent Process

Consent will be obtained in-person from a study PI, co-I, or coordinator. Comprehension will be ensured by allowing ample time for questions and discussion and verbally reviewing the information with the subject in addition to reviewing the written consent form. The discussion will take place at the Emory Sleep Center.

Compensation

Participants will be compensated \$25 for visit 1 (enrollment) and \$25.00 for the week 12 study visit (visit 5), for a total of \$50.

Statistical Analysis

Sample size will be 22 in each group. This sample size is sufficient to demonstrate a reduction in ESS of 4 points with amphetamine salts, assuming a standard deviation of change from baseline of 6.2 (35). This is

a conservative, but clinically significant, change in Epworth, compared to the observed change from baseline of 5.3 points in clinical trials of modafinil [weighted average from (15, 35, 36)]. This sample size provides 82.8% power to find a moderately large effect size for amphetamine salts. For non-inferiority, we will use a responder definition of those achieving a 25% reduction in ESS, a data-driven minimal clinically significant change in patients with narcolepsy (29). Assuming 80% of participants meet this threshold, 22 participants per group will provide 80% power to a non-inferiority limit of 30% (37, 38).

Intention-to-treat analyses will be performed, using last observation carried forward in the event of participant drop-out. The change in ESS at week 12 from baseline will be compared between the two treatment groups via t-test (compared for unequal variances if necessary) and will be evaluated on a hypothesis of non-inferiority. Similar analyses will be performed on secondary outcomes, considering the proportion of responders in each treatment arm who rate themselves "much improved" or "very much improved". Categorical outcomes, including these PGI-C proportions and adverse events, will be compared using Chisquare or Fisher exact test. Exploratory analyses will evaluate response at week 4 and week 8 between the two medications groups, to determine if there is a difference in time to symptom control.

Considering each medication separately, predictors of response will be assessed using logistic regression. The main predictor of interest will be hypersomnia diagnosis, i.e., narcolepsy type 2 or idiopathic hypersomnia. Other predictors, to be considered in separate, exploratory regression models, include: MSLT mean sleep latency, MSLT number of SOREMs, sex/gender, baseline ESS, age, and comorbidities. Significant predictors in univariate models will be combined in a multivariate model. Although the investigative team has extensive clinical trial and statistical experience, additional statistical consultation will be provided as needed through Emory's CTSA consultation program.

Data Safety Monitoring and Reporting

Participants will be screened for medication contraindications (detailed above) prior to participation, to minimize risk of serious drug adverse reactions. During the study, participants will be encouraged to report any adverse events and will be provided with 24-hour contact information with which to do so. Participants will be systematically assessed for expected and idiosyncratic adverse reactions every four weeks during participation. [name] will review routine adverse event logs at least once a week. For adverse events reported between routine assessments, [name] or [name] will review immediately and provide guidance to the participant on if and how to adjust study mediation (e.g., discontinue in the case of a severe adverse reaction) and any additional care that should be sought (e.g., urgent or emergency care). [name] will convey any reportable events to the Emory IRB using the standard reporting timeline, based on event severity. [name] will also oversee protocol compliance and data accuracy. She will perform reviews of case report forms every four weeks, to ensure consistency with protocol and data entry accuracy. [name] and the study coordinator will work together to complete the Emory IRB's "EU Self-Monitoring Tool" (available at http://www.ctac.emory.edu/clinical_trial_guidebook/data_and_safety_monitoring_plans.html) every six months.

Confidentiality

Data collection will be performed using the REDCap research tool, including online assessments. REDcap provides secure, web-based applications that offer easy data manipulation with audit trails for reporting, monitoring, and querying patient records and an export mechanism to statistical programs (e.g., SAS). REDcap servers are housed in a local data center at Emory University and all web-based information transmission is encrypted. REDcap was developed specifically to be compliant with HIPAA-security guidelines. Paper records (e.g., consent forms) will be stored in a locked office. When subsets of data are

housed on individual computers for data analysis and manuscript preparation, the minimum amount of identifiers will be included and computers will be encrypted.

Citations

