In contrast, trials that incorporate degrees of pragmatism (19, 20) can help overcome some of these obstacles to increase generalizability and more clearly guide clinical practice. Inclusion criteria are intentionally broad, allowing inclusion of patients with clinically-important comorbidities (e.g., mood disorders among narcolepsy patients), to better mimic the range of patients encountered in clinical practice (13, 20). Two active treatments may be directly compared, rather than employing a placebo (13), so that patients considering enrollment can be assured that they will receive an active treatment for the duration of the study. The majority of measures collected are those that can be embedded into clinical practice (20).

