Participants will be randomized to receive a 12-week treatment course with either modafinil or amphetamine-dextroamphetamine. Both are US FDA approved for the treatment of narcolepsy, although are considered off-label use for idiopathic hypersomnia. The main risks of participation are from the study medications (which are the standard of care). Common adverse events include: headache, nervousness, anxiety, insomnia, anorexia, xerostomia, palpitations/tachycardia, emotional lability, agitation. Less commonly reported adverse events included: nausea/vomiting, rhinitis, diarrhea, dizziness, dyspepsia, pharyngitis, HTN, chest pain, vasodilation, elevated ALT or AST, paresthesia, depression, constipation, abdominal pain, weight loss, motor/phonic tic exacerbation, dyspnea, diaphoresis, dysmenorrhea, impotence, visual disturbance, restlessness, tooth disorder, photosensitivity. Rare but serious AEs include:

- dependency, abuse
- psychosis
- mania
- aggressive behavior
- sudden death
- myocardial infarction
- stroke
- HTN
- cardiomyopathy (long-term use)
- seizures
- hypersensitive reaction, multi organ
- anaphylaxis
- Stevens-Johnson syndrome

- toxic epidermal necrolysis
- priapism
- peripheral vasculopathy
- Raynaud phenomenon
- Growth suppression (long-term use, peds pts)
- rhabdomyolysis
- withdrawal signs and symptoms if abrupt discontinuation (prolonged with high dose use)
- angioedema
- drug reaction with eosinophilia and systematic signs and symptoms
- hallucinations
- suicidal ideation

However, the medications being used in this study are currently standard of care for narcolepsy, being tested in this study for equivalency. Therefore, although there are risks to participation in this research, they are of the same magnitude of the risks patients take when seeking treatment for these disorders outside of this research. The benefit to be gained is a clearer understanding of the relative risks and benefits of these medications and the clinical features that can help predict response to treatment.

Community Participation

[name] consulted with leadership from the Hypersomnia Foundation and Narcolepsy Network in the initial submission of this work and will present results from the study at at least one meeting of one or both of these patient organizations following its completion.

Participant Selection

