This study will recruit up to 55 participants, with a sample size target of 44 participants who complete participation in the 12 week medication trial. Participants will be newly diagnosed, medication-naïve individuals, or formerly diagnosed, free of wake-promoting medication or willing to discontinue current wake-promoting medication with diagnoses of: narcolepsy type 2 or idiopathic hypersomnia.

Inclusion criteria will be: 1) narcolepsy type 2 or idiopathic hypersomnia; 2) age 18-65; 3) informed consent.

Exclusion criteria will be: 1) contraindication to modafinil or amphetamine salts (history of left ventricular hypertrophy, mitral valve prolapse, other cardiac structural abnormalities, severe cardiovascular disease, unstable angina, myocardial infarction, cardiomyopathy, severe arrhythmias, uncontrolled hypertension, severe hepatic impairment, substance abuse history, psychosis, glaucoma, Tourette's syndrome, and epilepsy); 2) obstructive sleep apnea (AHI > 15); 3) severe periodic limb movements of sleep with arousals (PLM arousal index > 30); 4) allergy to either of the study drugs; and 4) pregnancy or breastfeeding.

Participants who withdraw from study medication will be invited to complete remaining questionnaires/study visits.

Visit Schedule

Visit 1: Enrollment: After reviewing information about the study and confirming participation, subjects will answer questions about their sleep disorder and the symptoms experienced. This visit is expected to last about one hour. If participants are suspected of having a diagnosis of narcolepsy type 2 or idiopathic hypersomnia and have never had an overnight polysomnogram (PSG) and next-day MSLT, they will be scheduled for an

additional study visit to complete a PSG and MSLT before visit 3. If participants already have a confirmed diagnosis of narcolepsy type 2 or idiopathic hypersomnia and are taking certain stimulant medications they will be asked to wean off of this medication before and during the study. After weaning off of medicines, the participant will be given a four-week supply of one of the two study medications. The medication will be provided will be assigned randomly, the participant and the doctor will not be told which of the two study medications are given.

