Visit 2: Participants will only participate in this visit if they haven't had a sleep study prior to enrollment. Sleep testing: During this visit, participants will come to the Sleep Center for an overnight sleep study, during which they will be monitored with multiple wires on their body to measure sleep, breathing, and activity at night. The next day, they will remain at the Sleep Center until approximately 5 pm, taking naps five times during the day.

After these results are received and if the results are positive for a diagnosis of narcolepsy type 2 or idiopathic hypersomnia, participants will be given a four-week supply of one of the two study medications and will proceed with the remaining study visits. If the results are negative for narcolepsy type 2 or idiopathic hypersomnia, participants will be withdrawn from the study.

Visit 3 (four weeks medication dispensed at either Visit 1 or Visit 2): Complete questionnaires and pick up medication for the next four weeks (the same medication they have been taking already) at the Emory Sleep Center.

Visit 4 (four weeks after Visit 3): Complete questionnaires and pick up medication for the next four weeks (the same medication they have been taking already) at the Emory Sleep Center.

Visit 5 (four weeks after Visit 4): Meet with a study team member to discuss experience with the medication. Complete questionnaires and return any unused study drug.

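### Participants who skip Visit 2 have no scheduled pre-dose adverse-event record, and no new-or-worse rule limits what the Aim 2 comparison counts, so that comparison may be diluted

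*Combined protocol and SAP*

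**What the plan says.** Appendix 1 (Schedule of Study Visits) leaves the row "Adverse Experiences" blank at Visit 1 and marks it at Visits 2, 3, 4 and 5. The same table marks the Epworth scale, the Sleep Inertia Questionnaire and the CGI questionnaires at Visit 1.

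On Visit 2, the Visit Schedule says: "Participants will only participate in this visit if they haven't had a sleep study prior to enrollment". For those who attend, drug follows a positive result: "participants will be given a four-week supply of one of the two study medications and will proceed with the remaining study visits". For people already diagnosed and taking stimulants, the Visit 1 text says: "After weaning off of medicines, the participant will be given a four-week supply of one of the two study medications". No further visit is scheduled between weaning and the first dose. Study Design & Methods allows up to two weeks for discontinuation. It also waives PSG/MSLT while the sleep laboratory is closed, so entrants by that route have no sleep-study visit.

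Data Safety Monitoring and Reporting states: "Participants will be systematically assessed for expected and idiosyncratic adverse reactions every four weeks during participation". The risk text in Study Design & Methods states: "Common adverse events include: headache, nervousness, anxiety, insomnia, anorexia, xerostomia, palpitations/tachycardia, emotional lability, agitation". It also lists withdrawal signs and symptoms among the rare but serious risks.

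The analysis is one sentence in Statistical Analysis: "Categorical outcomes, including these PGI-C proportions and adverse events, will be compared using Chisquare or Fisher exact test". There is no definition of a treatment-emergent event, no reference to the first dose and no adjustment for baseline.

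**The concern.** Aim 2 compares the safety of the two drugs, and the Abstract says the results should inform shared decisions between them. Efficacy has a baseline for everyone, whereas adverse events have one only for those who attend Visit 2. Several of the expected reactions, such as headache, anxiety and insomnia, are non-specific and can be present without either drug. The Background section says that patients with comorbidities, mood disorders among them, are deliberately admitted.

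If a symptom present before the first dose is recorded at Visit 3 and counted, it adds to the rate in both arms. The same holds for a symptom of stopping previous medication. An event logged at Visit 2, before any drug, could also enter the comparison, because nothing in the analysis text excludes it. The result would be higher rates in both arms and a weaker contrast between them, in a trial with only 22 per arm. A pre-dose record cannot be recovered once dosing has begun.

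**Working it through.** **Who has a pre-dose record.** This follows from the Visit Schedule, the pandemic modifications and Appendix 1.

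| Entry route | Last scheduled visit before first dose | Adverse events assessed there? | First scheduled assessment |
|---|---|---|---|
| No earlier sleep study, tested at Visit 2 | Visit 2 | Yes | Visit 2, pre-dose |
| Earlier sleep study, no wake-promoting drug | Visit 1 | No | Visit 3, week 4 |
| Earlier sleep study, weaned off drug | Visit 1, then weaning | No | Visit 3, week 4 |
| Pandemic route, PSG/MSLT waived | Visit 1 | No | Visit 3, week 4 |

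The documents do not say how many participants fall in each row.

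**What dilution would cost.** The plan gives no adverse-event rate, safety margin or power for Aim 2, so there is no stated figure to reproduce. The only input from the documents is n = 22 per arm (Statistical Analysis). The rest is assumed:

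- drug-caused rates p of 10% and 40%;
- background prevalence b, equal in both arms and independent of the drug effect;
- a two-sided 5% Fisher exact test, with power from full enumeration of both binomial distributions.

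Two counting rules are compared:

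- Prior symptoms counted: observed rate = 1 − (1 − p)(1 − b).
- Only new events counted, and no prior symptom ever qualifies as worse (the least favourable case for the fix): observed rate = p(1 − b).

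For b = 30%, the first rule gives 1 − 0.9 × 0.7 = 37% and 1 − 0.6 × 0.7 = 58%. The second gives 0.1 × 0.7 = 7% and 0.4 × 0.7 = 28%.

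| b | Prior symptoms counted | Power | New events only | Power | Difference, either rule |
|---|---|---|---|---|---|
| 0% | 10% v 40% | 54.6% | 10% v 40% | 54.6% | 30 points |
| 10% | 19% v 46% | 36.4% | 9% v 36% | 47.9% | 27 points |
| 20% | 28% v 52% | 25.5% | 8% v 32% | 41.2% | 24 points |
| 30% | 37% v 58% | 18.9% | 7% v 28% | 34.4% | 21 points |
| 40% | 46% v 64% | 14.0% | 6% v 24% | 27.4% | 18 points |

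The absolute difference is (1 − b) times the difference in drug-caused rates under both rules, so in this case the new-events rule does not restore it. The rule keeps the rates low, and therefore less variable, and it keeps the ratio of the rates. At b = 30% the ratio is 28/7 = 4.0, as in the drug-caused rates, against 58/37 = 1.6 when prior symptoms count. The gain in power is 11.5, 15.7, 15.5 and 13.4 points at b = 10%, 20%, 30% and 40%.

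**Other assumed rates, at b = 30%.** For 10% v 30%, power is 8.9% with prior symptoms counted and 16.5% with new events only (7% v 21%); with no background it is 27.7%. For 10% v 50%, the figures are 34.3%, 54.6% (7% v 35%) and 78.6%.

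**False positives.** With the same true rate in both arms (10%, 30% or 50%), the Fisher test rejects in 1.4% to 2.4% of trials.

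**The case against.** The strongest reply is that the plan is silent rather than wrong. A blank adverse-event cell at a consent and history visit is not in itself a defect. Visit 1 records medical history, concomitant medication, a questionnaire packet whose contents are not shown, and questions on symptoms, so headache or anxiety may be captured there. Assignment is randomised and blinded, so background symptoms should balance. Even with no background, power is only 55% in the main illustration, so sample size limits Aim 2 in any case.

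Much of this stands, and it rules out four stronger readings that a reader might infer:

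- *That every participant lacks a baseline.* Visit 2 attendees are assessed before they receive drug. Only the missing analysis rule applies to everyone.
- *That existing symptoms are counted as drug events.* No section says so. They may be counted, because nothing excludes them.
- *That these complaints are common without treatment.* The documents give no untreated rates. The general statements on comorbidity make a zero background unlikely but do not fix a figure.
- *That a real safety difference is hidden, or that chance imbalance in prior symptoms creates a false one.* Randomised, blinded arms lose power without being tilted towards either drug, and the test's error rate already covers chance imbalance.

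The reply does not close the gap. The content of the Visit 1 history is unspecified, it is not tied to the assessment used at Visits 3 to 5, and no rule uses it to set prior symptoms aside. For weaned participants, Visit 1 also precedes washout. Balance between arms protects the error rate but does not undo dilution.

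**Conclusion.** The point holds in a limited form. Participants who skip Visit 2 have no scheduled pre-dose adverse-event record, and the Aim 2 analysis does not restrict events to those new or worse since the first dose. The consequence is possible inflation of both rates and a loss of power, not bias towards modafinil or amphetamine salts.

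Under the main assumptions (10% v 40%, background 10% to 40%), counting only new events is worth about 12 to 16 points of power, and power stays below 50% either way. The drug-caused rates, the background, its equality between arms and its independence of drug effect are all assumed; the documents fix none of them. Severity is minor to moderate. The primary and secondary efficacy outcomes are unaffected.

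**What to change.** Two changes are needed:

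1. **Appendix 1 and Visit Schedule.** Assess adverse experiences for every participant at the last contact before the first dose and after any washout. This may be Visit 1, Visit 2 or a remote contact, depending on the route. A mark at Visit 1 alone would come too early for those still to be weaned. Use the same assessment as at Visits 3 to 5.
2. **Statistical Analysis.** State that the Aim 2 comparison uses events that are new, or worse than the pre-dose record, from the first dose onward. Events logged at Visit 2 before dosing then serve as baseline.

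The cost is a few minutes per participant, one change to the schedule and one sentence in the analysis text. Participants already enrolled without a pre-dose record cannot be given one and should be shown separately. The change does not remedy the low power that comes from 22 per arm, so a non-significant Aim 2 result should not be read as evidence of equal safety.

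### The stated 82.8% power fits a within-arm test that is not planned, and the planned between-arm non-inferiority t-test on ESS change has no margin, alpha or power

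*Combined protocol and SAP*

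**What the plan says.** All the relevant text is under Statistical Analysis in the combined protocol and SAP, apart from the recruitment figure under Participant Selection.

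- **Sample size, continuous scale.** Twenty-two per group is called "sufficient to demonstrate a reduction in ESS of 4 points with amphetamine salts, assuming a standard deviation of change from baseline of 6.2". The 4 points are described as conservative "compared to the observed change from baseline of 5.3 points in clinical trials of modafinil". Then: "This sample size provides 82.8% power to find a moderately large effect size for amphetamine salts".
- **Sample size, responder scale.** "For non-inferiority, we will use a responder definition of those achieving a 25% reduction in ESS". With 80% of participants assumed to respond, "22 participants per group will provide 80% power to a non-inferiority limit of 30" per cent.
- **Analysis.** Week-12 change in ESS is to be "compared between the two treatment groups via t-test (compared for unequal variances if necessary) and will be evaluated on a hypothesis of non-inferiority". The responders defined in this paragraph are those with the two best PGI-C ratings. "Categorical outcomes, including these PGI-C proportions and adverse events, will be compared using Chisquare or Fisher exact test".
- **Analysis set.** "Intention-to-treat analyses will be performed, using last observation carried forward in the event of participant drop-out". Participant Selection allows up to 55 recruits in order to reach 44 completers.

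No significance level, sidedness or confidence level is stated anywhere in the document.

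**The concern.** The power statement and the planned test do not match. The 4 points and the 5.3 points are both changes from baseline within a single arm; neither is a difference between arms. Power for a within-arm change says nothing about how well the trial can compare amphetamine salts with modafinil. A fall from baseline in one arm also contains regression to the mean and expectation.

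The non-inferiority claim has a second gap. A t-test on mean ESS change can support non-inferiority only against a margin in ESS points, and none is given. The one stated limit is a difference in proportions, which cannot serve a test of means. If the sentence on categorical outcomes was meant to cover ESS responders, a chi-square or Fisher test of equality does not use the 30% limit either. The two paragraphs therefore offer two possible criteria on different scales. They could disagree, and the plan does not say which decides. Left open, that choice could be made after the data are seen.

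**Working it through.** **Inputs from the document:** 22 per arm; 4-point reduction; SD of change 6.2; 5.3-point modafinil change; 80% responders; 30% limit; up to 55 recruited, randomised 1:1. **Assumed:** every alpha below, because none is stated; equal SD in both arms; modafinil as the reference.

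**1. Reproducing the 82.8%.** Paired t-test, n = 22, 21 df, two-sided 5%, noncentral t:
- d = 4/6.2 = 0.645 gives power 82.3%.
- d rounded to 0.65 gives 82.8%, the stated figure.
- One-sided 5% gives 90.0%, which does not match.

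**2. The same inputs between arms.** SE = 6.2 × √(2/22) = 1.869, 42 df. Power for a 4-point difference is 55.2% at two-sided 5% and 67.7% at one-sided 5%. Neither matches. A two-sample test at one-sided 5% with d = 0.80 gives 83.3%, but that is 0.80 × 6.2 = 4.96 points, not 4.

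**3. Reproducing the responder calculation.** n per arm = (z_α + z_0.80)² × 2 × 0.8 × 0.2 / 0.3².
- One-sided 5%: 21.98, so 22 per arm. This matches.
- One-sided 2.5%: 27.91, so 28 per arm. Power with 22 per arm is 70.1%.
- With 27 per arm, power is 86.7% (one-sided 5%) or 78.7% (one-sided 2.5%).

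**4. Precision of the planned between-arm comparison,** half-width = t × 6.2 × √(2/n):

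| n per arm | SE | 95% CI half-width | 90% CI half-width |
|---|---|---|---|
| 22 (42 df) | 1.869 | 3.77 | 3.14 |
| 27 (52 df) | 1.687 | 3.39 | 2.83 |

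As shares of 5.3 points, the 95% half-widths are 3.77/5.3 = 71% and 3.39/5.3 = 64%. The 90% half-widths are 3.14/5.3 = 59% and 2.83/5.3 = 53%. The 27 per arm is a ceiling: it needs nearly all of the 55 recruits to be randomised and analysed. Any effect of LOCF on the SD is unknown.

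**5. Non-inferiority power of the t-test, for illustration only.** The plan gives no ESS-point margin. Taking 4 points with no true difference:

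| n per arm | One-sided 2.5% | One-sided 5% |
|---|---|---|
| 22 | 55% | 68% |
| 27 | 64% | 76% |

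With 22 per arm and no true difference, 80% power needs a margin of about 5.4 points (one-sided 2.5%) or 4.7 points (one-sided 5%). The first exceeds the whole 5.3-point modafinil change, and the second is 4.7/5.3 = 89% of it. If the planning values were true (4 against 5.3, a difference of 1.3), a 4-point margin would have 29% or 41% power.

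**The case against.** The plan does contain a complete non-inferiority criterion: a responder definition, an assumed rate, a limit, a power and a sample size, which agree with each other at one-sided 5%. The analysis paragraph follows directly and could be read as pointing back to it. That paragraph also speaks of response at weeks 4 and 8 and of predictors of response without redefining response, so the ESS responder may have been meant throughout. This is a fair reading of the intent. It does not remove the problem, because the text attaches non-inferiority to a t-test of mean change, and a limit on a difference in proportions cannot decide that test.

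The within-arm origin of the 82.8% is inferred, and the exact match needs a rounded effect size. That stands as a caveat, and the sponsor should confirm the origin. Of the alternatives tried, the only one that comes close to 82.8% needs about 5 points instead of the stated 4.

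The 95% interval is the less favourable convention. The plan's own responder calculation works only at one-sided 5%, which corresponds to a 90% interval, so the half-width would be 2.8 to 3.1 points. Both are shown above, and even the narrower one is more than half of the 5.3-point modafinil change.

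**Conclusion.** The concern holds. No sum is wrong: the 82.8% and the responder sample size can both be reproduced at plausible unstated alphas. But the 82.8% is not the power of the comparison the plan makes. On the same inputs a between-arm t-test has 55% (two-sided 5%) or 68% (one-sided 5%) power for a 4-point difference. As written, the t-test on the primary outcome cannot give a non-inferiority decision, and the 30% responder limit is not tied to any analysis described.

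At SD 6.2, an observed difference of zero would still be compatible with amphetamine salts being 3.4 to 3.8 points worse (95% interval, 27 down to 22 per arm). These figures rest on the plan's SD applying to both arms and on assumed alphas. The responder power also depends on alpha: 80.0% at one-sided 5% and 70.1% at one-sided 2.5%, with 22 per arm.

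**What to change.** Keep the sample size and amend the text.

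1. Confirm how the 82.8% was obtained and state its test and alpha. If it is within-arm power for amphetamine salts, label it so and say that it does not support the between-arm comparison.
2. Before unblinding, reconcile the sample-size and analysis paragraphs by saying which was intended:
   - **(a)** The 25%-reduction responder comparison carries non-inferiority, with the 30% limit, a stated alpha, the power at that alpha, and a confidence interval for the difference in proportions. The t-test is then reported as an estimate with its confidence interval. The sections that name ESS change as the primary outcome would need to agree with this.
   - **(b)** The t-test carries non-inferiority, with a justified margin in ESS points, alpha and sidedness, and the power at that margin. The responder comparison is labelled supportive.
3. Report the between-arm precision: a 95% half-width of about 3.8 points at 22 per arm, and about 3.4 at 27 with a note that this is the best case. If one-sided 5% is chosen, give the 90% figures (3.1 and 2.8) as well.

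The cost is wording and one decision, with no extra patients. The downside is that the stated power for the primary ESS comparison becomes less favourable. Under (a) the conclusion also rests on a dichotomised score.
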